## **14.2. Methods and Timing of Safety Assessments**

Serial measurements of safety will be performed at baseline and at scheduled intervals throughout the duration of the study as outlined in [Table 2](#). All scheduled visits will have a  $\pm 3$  day window unless otherwise stated. Abnormalities will be captured as adverse events. The adverse event of flare reaction, which may mimic disease progression, may render the efficacy assessments not evaluable at the corresponding visit(s). Cause of death is to be recorded in the CRF and the subject's medical record.

## **14.3. Recording and Reporting of Adverse Events**

The recording and reporting of adverse events is described in [Appendix 22.1](#).

[REDACTED]

[REDACTED]

- [REDACTED]
- [REDACTED]
- [REDACTED]
- [REDACTED]
- [REDACTED]
- [REDACTED]
- [REDACTED]

[REDACTED]

[REDACTED]

## 16. STATISTICAL ANALYSES

### 16.1. Statistical Overview

The objective of the statistical analysis will be to compare the efficacy and safety of lenalidomide versus placebo as maintenance therapy in subjects with relapsed or refractory B-cell chronic lymphocytic leukemia (CLL) having achieved PR or better after second-line therapy.

Overall survival (OS) will be the primary endpoint for the protocol following amendment #10. This analysis will be performed at the completion of the study. It is estimated that at least 160 subjects across both treatment arms have died at the time of analysis (yielding 80% power to detect a 61.3% improvement in median OS for a two-sided test at 0.025 level allowing for one interim analysis).

### 16.2. Study Population Definitions

#### 16.2.1. Intent-to-Treat Population

The primary efficacy analysis will be performed on the intent-to-treat (ITT) population, which will include all subjects who were randomized.

#### 16.2.2. Safety Population

All randomized subjects who receive any study drug will be included in the safety analyses.

#### 16.2.3. Subgroup Analyses

In addition to analyses that include all subjects, analyses will be performed to compare treatments within the following stratification subgroups:

- Response to second-line induction chemotherapy (PR, CRi or CR versus MRD-negative CR)
- Age ( $\leq 70$  years versus  $> 70$  years)
- Presence of at least one of the following poor prognostic factors: 11q deletion, 17p deletion, unmutated IgVH or  $\beta 2M > 4.0$  mg/L (Yes versus No versus Unknown)

Additional subgroups may be examined, as needed based on regulatory and clinical requests.

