## 8. INVESTIGATIONAL PLAN

### 8.1. Overall Study Design

CC-5013-CLL-002 is a phase 3, multicenter, randomized, placebo-controlled, parallel-group study that will compare the efficacy and safety of oral lenalidomide maintenance therapy to that of placebo in subjects with B-cell CLL who achieved at least partial response (PR) with second-line therapy. The primary efficacy objective of this study is to demonstrate superiority of lenalidomide over placebo in prolonging OS due to continued therapy, for all subjects, including subjects with or without poor prognostic factors, subjects of various ages and subjects with PR, nodular partial response (nPR), complete response with incomplete bone marrow recovery (CRi), complete response (CR), and minimal residual disease (MRD)-negative CR. All subjects randomized to the lenalidomide arm, including those subjects who do not improve their response (PR, nPR, CRi, or CR) and subjects who do not have the opportunity to improve their response further (MRD-negative CR) will be treated up to disease progression with the objective to demonstrate prolongation of OS.

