### **16.3.3. Efficacy Analyses**

Kaplan-Meier product limit methods will be used to estimate the survivorship functions for the time-to-event endpoints (eg, OS, and PFS2). A two-sided log-rank test stratified by the 3 strata used in the randomization will be used as the primary analytic method to compare survivorship functions for time-to-event variables in the 2 treatment groups. In terms of the survivorship functions for each treatment group, the hypotheses of interest were:

$$H_0: F_A(t) = F_P(t) \text{ for all } t$$

Versus

$$H_1: F_P(t) \neq F_A(t) \text{ for all } t$$

where  $F_P$  is the survivorship function for placebo and  $F_A$  is the survivorship function for lenalidomide.

Median OS will be estimated using Kaplan-Meier estimates, and the 95% confidence intervals (CI) will be computed using the method of Brookmeyer and Crowley. Hazard ratio will be calculated using Cox model stratified for the 3 strata (ie, response to second-line induction chemotherapy, age, and presence of at least one prognostic factor) to account for the stratified randomization. The Cox model will also be used to identify prognostic factors.

Cross-tabulations will be provided by treatment group to summarize improvements from the best response during induction therapy.

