## 16.9. Sample Size and Power Considerations

For OS, a 61.3% improvement in median survival from randomization, from 3 years for placebo to 4.83 years on lenalidomide is considered clinically relevant. The OS is assumed to be exponential with a constant failure (hazard) rate. When the total number of events is approximately 160 over both treatment arms, then a two-sided log-rank test with an overall significance level of 0.025 (allowing for one interim analysis) would have 80% power to detect a hazard rate ratio of 0.62 (that is, if the survival curves are exponential, to detect a 61.3% difference in the median OS in the 2 arms). To ensure timely completion of the study, 320 subjects will be enrolled, 160 in each treatment arm. Enrollment will close once 320 subjects are randomized or 160 adjudicated PFS events are reached, whichever comes first.

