11.3. Subgroup Analysis

The effect of treatment on the efficacy endpoints of PFS and OS will be compared between treatment arms within subgroups defined by the following variables:

- Age group (≤ 70 , > 70 years)
- Response to 2nd line therapy: (PR, nPR, CRi or CR *versus* MRD-negative CR)
- Presence of at least one of the following poor prognostic factors: 11q deletion, 17p deletion, unmutated IgV_H or $\beta 2M > 4.0$ mg/L (Yes versus No versus Unknown)

The methods described in Sections 11.1.1 and 11.2.1 for the endpoints of PFS and OS respectively, will be used for each subgroup.

[REDACTED]

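### The subgroup analyses compare arms within each level, and no legible text specifies an estimate of how the treatment effect differs between levels

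*Protocol*

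**What the plan says.** Protocol 16.2.3 (Subgroup Analyses) states that "analyses will be performed to compare treatments within the following stratification subgroups" and lists the three randomization factors: response to second-line therapy (two levels), age (two levels) and presence of a poor prognostic factor (Yes, No, Unknown). It adds: "Additional subgroups may be examined, as needed based on regulatory and clinical requests".

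SAP 11.3 (Subgroup Analysis) says that PFS and OS "will be compared between treatment arms within subgroups defined by the following variables", and names the same three factors. On method it says: "The methods described in Sections 11.1.1 and 11.2.1 for the endpoints of PFS and OS respectively, will be used for each subgroup". Section 11.1.1 contains the log-rank test, Kaplan-Meier estimates with medians and confidence intervals, and the Cox hazard ratio. Section 11.2.1, cited for OS, is in fact tumor response, compared by Van Elteren's test. The OS method is in Section 11.1.2.

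Protocol 8.1 frames the primary efficacy objective as superiority in OS "for all subjects, including subjects with or without poor prognostic factors, subjects of various ages" and depths of response. Those are the same three factors.

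The Cox model has one other stated use in Protocol 16.3.3 and SAP 11.1.1, which is to look for prognostic factors. That concerns the association of a factor with outcome, not a difference in treatment effect between its levels.

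**The concern.** Whether an effect differs between two groups of patients is a question about the difference between two estimates. A p-value from each group separately does not answer it: one level can cross the threshold and the other miss it only because they contribute different numbers of deaths, or by chance. The three factors give 2 + 2 + 3 = 7 within-level comparisons for OS, each resting on a share of about 160 deaths. The SAP repeats them for PFS, and further subgroups may be added on request.

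The objective invites the reader to look across exactly these factors. Without a planned contrast or a rule for reading discordant results, a drug that works equally well everywhere can easily appear to work only in, say, younger patients or those without poor prognostic factors.

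**Working it through.** **Inputs.** Hazard ratio 0.62, about 160 deaths, 1:1 allocation and overall two-sided alpha 0.025 for OS (Protocol 16.9, SAP 6.1 and 11.1.2). Neither document gives a split of deaths by subgroup or a subgroup alpha, so both are varied below.

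**1. The plan's own figure.** With d deaths and 1:1 allocation, power ≈ Φ(|ln HR|·√d/2 − z), where |ln 0.62| = 0.478. Overall: 0.478 × √160/2 = 3.023; 3.023 − 2.241 = 0.782; Φ = 78.3%. The plan states 80%, so its figure is reproduced to within two points.

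**2. Two levels, the same true hazard ratio of 0.62 in both.** If the powers are p1 and p2 and the levels are independent, P(exactly one significant) = p1(1 − p2) + p2(1 − p1).

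Example, 80/80 at two-sided 0.05: 0.478 × √80/2 = 2.138; 2.138 − 1.960 = 0.178; Φ = 0.571. Exactly one: 2 × 0.571 × 0.429 = 0.490.

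Example, 128/32 at 0.05: powers 0.772 and 0.272. Exactly one: 0.772 × 0.728 + 0.272 × 0.228 = 0.624.

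| Alpha (two-sided) | Deaths per level | Power per level | Both | Exactly one | Neither |
|---|---|---|---|---|---|
| 0.05 | 80/80 | 57.1%, 57.1% | 32.6% | 49.0% | 18.4% |
| 0.05 | 112/48 | 71.6%, 38.1% | 27.2% | 55.1% | 17.6% |
| 0.05 | 128/32 | 77.2%, 27.2% | 21.0% | 62.4% | 16.6% |
| 0.05 | 144/16 | 81.8%, 15.8% | 12.9% | 71.8% | 15.3% |
| 0.025 | 80/80 | 45.9%, 45.9% | 21.0% | 49.7% | 29.3% |
| 0.025 | 112/48 | 61.3%, 27.9% | 17.1% | 55.0% | 27.9% |
| 0.025 | 128/32 | 67.8%, 18.7% | 12.7% | 61.2% | 26.2% |
| 0.025 | 144/16 | 73.5%, 9.9% | 7.3% | 68.8% | 23.9% |

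By simulation, among trials in which the overall OS test is significant, exactly one level is significant in 54% to 84% across these splits and alphas.

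**3. The three-level prognostic factor.** For the splits tried (equal; 60:30:10; 50:30:20), a mixed pattern, with some but not all levels significant, occurs in 64% to 78% of trials.

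**4. All three factors together.** With deaths spread evenly over the 12 cells, simulation gives a mixed pattern on at least one factor in 83% of trials (0.025) or 86% (0.05).

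**5. A between-level contrast.** The difference in log hazard ratios has standard error √(4/d1 + 4/d2). Tested at two-sided 0.05, it flags a uniform effect 5% of the time per factor, whatever the split. Its sensitivity is limited:

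- 80/80: SE = √0.1 = 0.316. The 95% CI runs a factor of exp(1.96 × 0.316) = 1.86 either side of the estimate. Power for a ratio of hazard ratios of 0.62 is Φ(0.478/0.316 − 1.96) = 33%. Power reaches 80% only for a ratio of exp(−2.80 × 0.316) = 0.41.
- 128/32: SE = √0.15625 = 0.395. The CI factor is exp(1.96 × 0.395) = 2.17, and power for a ratio of 0.62 is Φ(0.478/0.395 − 1.96) = 23%.

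**The case against.** Much of the case on the other side stands.

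- A reader might infer that repeated log-rank tests are the only subgroup method. They are not. SAP 11.3 imports the whole of Section 11.1.1, so within-level hazard ratios are already planned. What none of these methods does is compare one level with another.
- A reader might infer that the plan judges consistency by subgroup p-values. Neither document says so. There is no consistency rule, subgroup alpha or subgroup claim, and comparing arms within a level can be met by reporting estimates. The percentages above therefore describe what happens if p-values are read as significant or not. The plan does not prescribe that reading, but does nothing to prevent it.
- A reader might infer that the trial has no interaction analysis at all. Only legible text can be checked. The protocol's contents list has blacked-out entries between 16.5 and 16.7 and between 16.7 and 16.9, and a redacted block follows SAP 11.3. The second copy of the protocol synopsis mentions exploratory work relating biomarkers, cytogenetics and age to survival, but not a contrast of treatment effects.
- The objective's wording may simply describe the randomized population, and the efficacy rules in SAP 11 use only overall PFS and OS. No primary conclusion depends on a subgroup result.
- Making the interaction test the arbiter of consistency would replace one misreading with another. At 23% to 33% power, a non-significant result would often accompany a real difference.

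What remains is that the legible plan has no estimate of the quantity needed to discuss differences between subgroups, and it can be had from data already collected.

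**Conclusion.** The point holds as a low-cost improvement, not as a flaw in the primary analysis. The legible plan gives within-level results on three factors that the objective names, with no between-level contrast and no guidance on discordant results. Under a uniform hazard ratio of 0.62 with 160 deaths, exactly one of two levels is significant in about 49% to 72% of trials at two-sided 0.05, or 50% to 69% at 0.025. Even an equal split gives about half.

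These figures rest on assumed splits from 80/80 to 144/16, an assumed subgroup alpha, and the usual normal approximation to the log-rank test. They show that within-level p-values cannot tell a uniform effect from a selective one. They do not show that the sponsor intends to read the results that way, and the redactions prevent saying that no interaction analysis was ever planned.

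**What to change.** In SAP 11.3, and in Protocol 16.2.3 if it is amended:

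1. For each stratification factor, coded as at randomization, fit a Cox model with treatment, the factor and their interaction. Report the ratio of hazard ratios with its 95% CI and the interaction p-value. The three-level prognostic factor gives two ratios and a joint test.
2. Show these beside the within-level hazard ratios and confidence intervals in a forest plot, labelled exploratory.
3. State that neither within-level p-values nor a non-significant interaction will be used to claim or deny consistency.
4. Correct the cross-reference for the OS method from Section 11.2.1 to Section 11.1.2.

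The cost is a short SAP edit and a few lines of code. It needs no new data and no extra events, and leaves the primary test and its alpha unchanged. The drawback is the low power of the interaction test shown above, which is why the ratio and its interval should carry the interpretation.

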### 16.3. Efficacy Evaluation

#### 16.3.1. Primary Endpoint

##### Overall Survival (OS)

Overall survival is calculated as the time from randomization to death from any cause. OS will be censored at the last date that the subject was known to be alive for subjects who were alive at the time of analysis and for subjects who were lost to follow-up before death was documented.

The analysis of OS will include survival information for all randomized subjects. Subjects who discontinued from the treatment phase of the study and who had possibly received other anti-cancer therapies and then subsequently died will be included in the analysis as death. However, sensitivity analyses will be performed in which these subjects will be censored at the date of the first dose date of the anti-cancer therapy.

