#### Amendment #11:

Subjects currently on lenalidomide treatment will discontinue lenalidomide treatment immediately and complete the Treatment Discontinuation assessment. The subjects will then transition to the survival follow-up period.

Eligible subjects must have been treated with a purine analog-, a bendamustine-, an anti-CD20 antibody-, or a chlorambucil-based regimen in first and/or second line and must have achieved at least PR to second-line induction therapy of sufficient duration. Alemtuzumab- containing regimens will also be allowed for those patients with 17p deletion. Subjects who achieve stable disease (SD) only or who develop progressive disease (PD) at any time during induction therapy will not be eligible for participation in this study.

Approximately, three hundred twenty (320) subjects with PR, nPR, CRi, CR or MRD-negative CR will be enrolled and randomized (1:1) into two arms: placebo daily or lenalidomide 2.5 mg daily on days 1-28 of the first cycle. If the 2.5 mg dose level is well tolerated, escalation to 5 mg daily on days 1-28 of each 28-day cycle is permitted starting with the second cycle. If a subject develops a Grade 1 or 2 adverse event, the drug may be interrupted until resolution, however the subject must complete one full cycle at the 2.5 mg dose level prior to escalation to the 5 mg dose level. For those subjects who tolerate the 5 mg dose without unacceptable toxicity, escalation to 10 mg daily on days 1-28 of each 28-day cycle after 5 continuous cycles at 5 mg will be permitted. Each treatment arm will be stratified according to 1) the response to second-line induction therapy (PR, nPR, CRi or CR versus MRD-negative CR); 2) age ( $\leq 70$  versus  $> 70$  years); and 3) presence of at least one of the following poor prognostic factors: 11q deletion, 17p deletion, unmutated IgVH or  $\beta 2M > 4.0$  mg/L (Yes versus No versus Unknown).

The subjects randomized to the lenalidomide treatment will continue to receive lenalidomide up to PD. For those subjects who discontinue therapy for reasons other than PD (ie, unacceptable toxicity) they will transition to the survival follow-up period.

Subjects who discontinued from the study drug will be followed every 24 weeks for survival, subsequent CLL therapies, response to next therapy and progression following next therapy, and

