**After Study Discontinuation:**

Upon discontinuation of study drug, subjects will be followed every 24 weeks for survival, information on other CLL treatments, response to next therapy and progression following next therapy, and second primary malignancies (reported as SAEs). Subjects will be followed until all subjects in the study have been followed for at least 5 years from the last randomization, October 2020 (or have died/become lost to follow-up before 5 years).

FCBP with regular menstrual cycles discontinued from treatment must have a pregnancy test on day 28 after the treatment discontinuation visit. FCBP with irregular cycles discontinued from treatment must have a pregnancy test on days 14 and 28 after the treatment discontinuation visit.

SAEs will continue to be collected for the first 30 days after the treatment discontinuation visit. Following 30 days post the treatment discontinuation visit, only SAEs related to maintenance therapy will be collected for the study duration. Second primary malignancies must be reported as SAEs. This includes any second primary malignancy, regardless of causal relationship to study medication, occurring at any time for the duration of the study, from the time of signing the informed consent up to and including progression free follow-up and survival follow-up.

[REDACTED]

[REDACTED]

[REDACTED]

[REDACTED]

[REDACTED]

[REDACTED]

[REDACTED]

[REDACTED]

[REDACTED]

[REDACTED]

[REDACTED]

[REDACTED]

[REDACTED]

[REDACTED]

[REDACTED]

[REDACTED]

[REDACTED]

[REDACTED]

[REDACTED]

[REDACTED]

[REDACTED]

[REDACTED]

[REDACTED]

[REDACTED]

[REDACTED]

[REDACTED]

[REDACTED]

[REDACTED]

[REDACTED]

[REDACTED]

[REDACTED]

[REDACTED]

[REDACTED]

[REDACTED]

[REDACTED]

[REDACTED]

[REDACTED]

[REDACTED]

[REDACTED]

[REDACTED]

[REDACTED]

[REDACTED]

[REDACTED]

[REDACTED]

[REDACTED]

[REDACTED]

[REDACTED]

[REDACTED]

[REDACTED]

[REDACTED]

[REDACTED]

[REDACTED]

[REDACTED]

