6. GENERAL STATISTICAL CONSIDERATIONS

6.1. Sample Size

For OS, a 61.3% improvement in median survival from randomization, from 3 years for placebo to 4.84 years on lenalidomide is considered clinically relevant. For PFS, a 61.3% improvement in median time to progression from randomization, from 20 months for placebo to 32.3 months on lenalidomide is considered clinically relevant. The OS and PFS distributions are assumed to be exponential with a constant failure (hazard) rate. When the total number of events is approximately 160 over both treatment arms, then a two-sided log-rank test with an overall significance level of 0.025 (allowing for the co-primary endpoints) would have 80% power to detect a hazard rate ratio of 0.62. To ensure timely completion of the study, 320 subjects will be enrolled, 160 in each treatment arm.

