11.1. Co-primary Endpoints and Analysis

11.1.1. Progression Free Survival

Progression-free survival will be calculated as the time from randomization to the first documented progression confirmed by a blinded, independent Response Adjudication Committee or death due to any cause during or after the treatment period, whichever occurs first. The progression date will be assigned to the earliest time when any progression is observed without prior missing assessments. If withdrawal of consent or lost to follow-up occurs before documented progression or death, then these observations will be censored at the date when the last complete tumor assessments determined a lack of progression.

For subjects who do not develop progressive disease at the time of analysis, if the response from the last visit was ‘not evaluable’, the most prior visit date with complete evaluation indicating no progressive disease will be used as the censor date. These rules are based on FDA guidance for cancer trial endpoints [REDACTED] and the following table specifies the application of the guidance for various common situations for the calculation of PFS.

Detailed decision rules for the primary and a sensitivity analysis of PFS are summarized in the following tables:

Table 2: Primary Analysis of PFS

Situation	Date of Progression or Censoring	Situation Outcome
No baseline tumor assessments	Randomization	Censored
Progression documented between scheduled visits	Earliest of: 
 • Date of physical examination for lymphadenopathies, spleen and liver showing: 
 ○ appearance of new lymphadenopathies or new organ infiltration or ○ increase by 50% or more in the greatest determined diameters of previously existing lymphadenopathies ○ increase by 50% or more in liver or spleen size • Date of lab test showing 50% or more increase in lymphocytes • Date of post-treatment lab test showing occurrence progression of cytopenia attributable to CLL • Date of test confirming transformation to a more aggressive histology 	Progressed
No progression	Date of last adequate assessment with evidence of no progression	Censored
Study discontinuation for reasons other than disease progression	Date of last adequate assessment with evidence of no progression	Censored
New anticancer treatment started with no claim of progression	Date of last adequate assessment with evidence of no progression prior to the start of new anticancer treatment	Censored

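### The OS sensitivity analysis, as worded, censors at next therapy only subjects who later died; survivors on the same therapy stay at risk, which distorts its hazard ratio

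*Protocol*

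**What the plan says.** Protocol 16.3.1 sets a general rule first: "OS will be censored at the last date that the subject was known to be alive for subjects who were alive". That refers to status when the analysis is done, and subjects lost to follow-up are handled likewise. It then covers the primary analysis. Subjects who left the treatment phase and "who had possibly received other anti-cancer therapies and then subsequently died will be included in the analysis as death" count as events. The next sentence adds the supportive analysis: "sensitivity analyses will be performed in which these subjects will be censored at the date of the first dose date of the anti-cancer therapy".

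SAP 11.1.2 uses the same wording, and so does section 17.3.1 in the second copy of the protocol text. No legible part of either document says how this analysis treats a subject who starts new therapy and is still alive.

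The SAP's progression-free survival (PFS) rule is built differently. In Table 2 of section 11.1.1 the trigger is "New anticancer treatment started with no claim of progression", so a subject is censored for starting treatment, not for what happened later.

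**The concern.** The only group that the words for the censored subjects can refer to is the one in the sentence before: "Subjects who discontinued from the treatment phase of the study and who had possibly received other anti-cancer therapies and then subsequently died". Membership requires death. Whether a subject is censored at next therapy therefore depends on the outcome being analysed.

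Two subjects who start the same therapy on the same study day are treated differently. The one who dies later is censored on that day and loses the event. The one who survives stays in the risk set until last contact, although no death after next therapy can be counted any longer. Each arm's apparent death rate falls by an amount that depends on how early its subjects start next therapy and how many of them survive. If the arms differ in either respect, the hazard ratio moves for a reason unrelated to survival.

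The analysis exists to show whether the OS result depends on later therapy. Maintenance treatment is meant to delay progression, so earlier next therapy on placebo is a likely pattern. The supportive result could then disagree with the primary one because of the wording alone. PFS2 also looks past the first progression, but it is a separate endpoint and does not replace this check.

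**Working it through.** **Inputs from the documents.** 160 subjects per arm, analysis at about 160 deaths, exponential OS, HR 0.62, two-sided 0.025 (Protocol 16.9). OS medians 3 vs 4.84 years (SAP 6.1; 3/0.62 = 4.84). Planned PFS medians: "from 20 months for placebo to 32.3 months on lenalidomide is considered clinically relevant" (SAP 6.1).

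**Assumptions.** The documents give no next-therapy times. The planned PFS medians stand in for them and are varied below. Next therapy is independent of death, and the death hazard is the same before and after it. Censoring everyone is then unbiased, and the contrast isolates the wording.

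**The plan's own figure.** Power at 160 deaths is Φ(√160/2 × |ln 0.62| − 2.241) = Φ(3.023 − 2.241) = 78.3%, close to the stated 80%.

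**Step 1: arithmetic with a common follow-up τ.** Let λ be the death hazard and ν the next-therapy hazard. Per subject:

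- time at risk up to death, next therapy or cutoff: P = (1 − e^(−(λ+ν)τ))/(λ+ν)
- deaths before next therapy: D = λP
- survivors' time after next therapy: E = e^(−λτ) × [τ − (1 − e^(−ντ))/ν]

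Censoring everyone gives the rate D/P = λ, which is correct. The written rule gives D/(P + E). For τ = 3 years:

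- Placebo, OS median 3 years, next therapy 20 months: λ = 0.2310, ν = 0.4159; 0.3059/(1.3238 + 0.6430) = 0.1555.
- Lenalidomide with no OS effect, 32.3 months: λ = 0.2310, ν = 0.2575; 0.3637/(1.5742 + 0.4551) = 0.1792. Ratio 0.1792/0.1555 = **1.15**; truth 1.00.
- Lenalidomide with OS median 4.84 years, 32.3 months: λ = 0.1432, ν = 0.2575; 0.2500/(1.7455 + 0.5923) = 0.1069. Ratio **0.69**; truth 0.62.
- Lenalidomide with OS median 4.84 years, 20 months: λ = 0.1432, ν = 0.4159; 0.2083/(1.4543 + 0.8369) = 0.0909. Ratio **0.58**; truth 0.62.

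E is larger relative to P when next therapy starts earlier and when more subjects survive. This is why the direction can go either way.

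**Step 2: simulation.** 160 per arm, unstratified Cox model. Ranges cover analysis at 160 deaths and a cutoff five years after the last randomization, mostly with 3-year uniform accrual (1 to 6 years for the 20/32.3 rows).

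| OS medians, years (placebo/lenalidomide) | Next therapy, months | HR as written | HR, everyone censored |
|---|---|---|---|
| 3/3 | 20/20 | 1.00 | 1.00 |
| 3/3 | 20/32.3 | 1.14–1.17 | 1.00–1.01 |
| 3/3 | 20/25 | 1.07–1.08 | 1.00 |
| 3/3 | 40/64.6 | 1.08–1.10 | 1.00 |
| 3/3 | 80/129.2 | 1.04–1.05 | 1.00 |
| 3/4.84 | 20/32.3 | 0.69–0.71 | 0.61–0.62 |
| 3/4.84 | 40/64.6 | 0.66–0.67 | 0.62 |
| 3/4.84 | 80/129.2 | 0.64 | 0.62 |
| 3/4.84 | 20/20 | 0.56–0.59 | 0.61–0.63 |

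In the second row at 160 deaths, the rule removes about 32 placebo and 23 lenalidomide deaths. It keeps about 54 and 41 survivors on new therapy at risk. A nominal two-sided 0.025 test then rejects in 6.8% of trials, against 2.6% when everyone is censored.

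**The case against.** **The text may only be loose.** It cannot be programmed with complete literalness. It refers to subjects who may have had other therapy, and some of them have no first dose date. Some interpretation is needed, and the PFS table suggests that the authors know the usual convention. They may well have meant to censor everyone. That is plausible, but nothing in either document says so, and the general rule does state what happens to subjects who are alive. A programmer following the text would produce the outcome-dependent version.

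**The contrast assumes next therapy is unrelated to prognosis.** In practice it often follows progression, so censoring everyone can itself be informative. This part stands. With an assumed shared gamma frailty (variance 0.5) and next therapy at 20 vs 32.3 months, the no-effect HRs are 1.17 to 1.19 as written and 1.07 to 1.09 with everyone censored. Under the design medians they are about 0.73 to 0.74 and 0.69 to 0.70, against an ITT HR of about 0.67. The wording then adds roughly 6 to 9%, instead of about 15%. The corrected rule is still closer to the ITT result in each case.

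**The effect is small against noise and gates nothing.** About 160 − 32 − 23 = 105 events remain, so the standard error of the log HR is near 2/√105 = 0.20, while ln 1.15 = 0.14. This also stands: in a single trial the shift is less than one standard error. It is nevertheless systematic, and a supportive analysis should not carry an avoidable bias.

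**Conclusion.** The concern holds. The stated rule selects subjects for censoring by their later death, and the SAP repeats it without correction. The primary ITT OS test counts every death and is not affected, so this is a point that should be fixed, not a threat to the main conclusion.

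The wording is certain; the size is conditional. It rests on assumed next-therapy times, exponential distributions and, for the larger figures, independence from prognosis. The shift is about 15% in the HR if next therapy follows the planned PFS medians, about 4 to 10% if it comes two to four times later, and nil if timing and death rates are equal. It works against lenalidomide when placebo subjects start next therapy earlier. It works in lenalidomide's favour when timing is equal and lenalidomide lowers mortality.

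**What to change.** In Protocol 16.3.1 (and its copy at 17.3.1) and SAP 11.1.2, define the censored group by the start of treatment: all subjects who start a new anti-cancer therapy, whether or not they later die, are censored at its first dose date. Subjects with no new therapy keep the primary OS rule. This also settles the case of subjects who only possibly had other therapy.

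Optionally, state that simple censoring may be informative, and add a version with inverse-probability-of-censoring weights if the follow-up data support it.

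The cost is one sentence in each document. No new data are needed, because Protocol 8.1 already provides for this: "Subjects who discontinued from the study drug will be followed every 24 weeks for survival, subsequent CLL therapies, response to next therapy".
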